4.5.3 Sensitivity analysis 3: Referral data

We will conduct a sensitivity analysis for outcomes relating to referrals (primary outcome and secondary outcome 4) for investigations regarding a possible prostate cancer. The sensitivity analysis will focus on prostate cancer as a referral to a urologist is one of the primary recommendations for follow-up delivered in the intervention. We expect that referral information will be difficult to capture in the EMR extracted data and not well recorded, leading to an underestimation of referrals to a specialist. Therefore, we will include diagnosis of prostate cancer, prostatitis or benign prostatic hyperplasia as a proxy for receiving a referral to a specialist (when the referral to the specialist was not reported in the EMR). For instance, for patients with one raised PSA who have no recorded referral to a urologist, will be coded for the sensitivity analysis as receiving a referral if they had a prostate diagnosis made by a urologist after they were identified as at risk of cancer. Same analysis outlined for the binary outcomes will be used for the sensitivity analysis. Other forms of cancer may be subject to this sensitivity analysis pending inspection of the data.

4.5.4 Sensitivity analysis 4: Symptoms

The outcome definition of appropriate follow-up includes any guideline concordant action taken by the GP including pathology tests, investigations, prescriptions, referrals and recording of relevant symptoms in the EMR. Due to the non-specific nature of some symptoms associated with cancer, we will conduct a sensitivity analysis for the primary outcome excluding symptoms as a measure of appropriate follow-up. The same analysis outlined for the binary outcomes will be used for the sensitivity analysis.

4.5.5 Sensitivity analysis 5: Missing outcome data

Due to the definition used to determine the study cohorts (i.e., patients determined to be at risk of an undiagnosed cancer) and the use of EMR data to determine outcomes, except for patients withdrawing from having their data for use in the Patron repository, we do not expect missing data and all eligible patients will be included. For the primary outcome and secondary outcomes 1-5 and 7, at the conclusion of the trial, anyone with a relevant follow-up or investigation will be considered to

have received guideline concordant care. If a relevant investigation or follow-up is not in the patient record, then they will be considered to not have received guideline concordant care.

 We expect the number of individual patients who withdraw their data from the study to be small. A sensitivity analysis will be conducted to assess the robustness of the missing data assumption using a pattern-mixture model if more than 10% of the eligible patients have missing responses either because of patient and/or practices withdraw from the trial.

4.5.6 Adherence-adjusted analysis

In the SAP for the CKD study we outlined a sensitivity analysis for incomplete adherence on the estimated intervention effects using a complier average casual effect (CACE) analysis¹⁶⁻¹⁸ for the primary outcome only. However, after the study investigators and data management team reviewed the data for adherence with the intervention protocol, we were unable to construct the indicators for incomplete adherence based on the level of FHT QI program integration within each practice. Thus, adherence-adjusted analysis will not be conducted. Three types of data were to be used as measures of adherence:

- 1) the number of practitioners actively engaged in the FHT trial compared to the number of computers with the FHT QI module installed/accessible by general practice clinicians as a proxy measure of the degree of access to the point of care clinical decision support tool.
- 2) the number of days that the QI module is active within each practice, that will take into consideration whether practices have experienced technical issues during the trial period.
- 3) the degree of engagement of general practices with the different components of the intervention (e.g., ECHO series, use of the FHT tool to create cohorts).

During data review, a series of observations were made that resulted in removal of adherenceadjusted analysis from the suite of analyses planned for the trial. Regarding the number of practitioners actively engaged in the FHT trial compared to the number of computers with the FHT QI module installed, the completeness and quality of the data collected was not considered to be of sufficient completeness, quality and/or reliability to use it as a proxy measure of access or engagement. Regarding the number of days that the QI module was active, the gathered data was incomplete and did not capture the range of technical issues experienced within practices. Data on major technical issues was available but such issues were rare, indicating that no practices experienced severe technical issues to a degree that indicated incomplete adherence. Finally, data collected regarding degree of engagement with intervention components was also considered to be insufficient for use as a proxy of adherence.

4.5.7 Exploratory/sub-group analyses

To evaluate the shorter time for follow-up in the open cohort, we will conduct a sub-group analysis in patients identified as at risk of an undiagnosed cancer, using the sub-groups of those identified at baseline (closed cohort), compared with those identified in the first 6 months after the trial start date (open cohort). Further sub-group analyses will be conducted for the primary outcome, such as the appropriate investigation for sex (male, female, other) and age at entry into the cohort. These exploratory analyses may be reported in part with the primary analysis or in a separate publication.

The statistical analysis for each subgroup will be conducted by including the subgroup variable and its interaction with the intervention as fixed effects to the regression models. Summary statistics will be presented for each sub-group within each study arm, as well as estimates for the intervention effects (appropriate to the outcome type) with a 95% confidence interval and a p-value corresponding to the

interaction term between the study arm and the subgroup variable. The estimates may also be displayed graphically using forest plots.

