2.2 Patient eligibility and exclusion criteria

Eligible patients will be identified as at risk of cancer by applying at least one or more of the following criteria:

At baseline – 4th October (**closed cohort**):

- Patients aged 50 to 80 years (inclusive) without a recorded GI, unspecified or metastatic cancer in the last 5 years who have one marker of anaemia (defined as Hb <130g/L in men and <115g/L in women or MCV <80fl or MCH <27pg or ferritin<30µg/L) in the past 6 months or two consecutive markers of anaemia in the past 12 months.
- 2. Males aged 40 to 80 years (inclusive) without a recorded diagnosis of lung, colorectal, gastrooesophageal or unspecific cancer in the previous 5 years or females aged 40 to 80 years old without a diagnosis of lung, colorectal, gastro-oesophageal, ovarian, endometrial or unspecific cancer in the previous 5 years who have one elevated plated count (defined as platelet count > 400×10^{9} /L) in the past 6 months or two consecutive elevated platelets counts in the past 12 months.
- 3. Males, aged 40-80, without a recorded diagnosis of prostate cancer with a raised PSA (defined as male aged 40-49 PSA > 2.0 ng/ml; male aged 50+ PSA> 3.0 ng/ml) in the past 6 months.

4th Oct 2021 - 4th April 2022 (**open cohort**):

- 4. Eligible patients not captured at baseline, with one or more markers of anaemia between October 4, 2021, and April 4, 2022.
- 5. Eligible patients not captured at baseline with an elevated platelet count between October 4, 2021, and April 4, 2022.
- 6. Eligible patients not captured at baseline with an elevated PSA between October 4, 2021, and April 4, 2022.

The terms closed and open cohort refer to when the patients were identified as at risk of cancer: at baseline, or during the first 6-months of the trial, respectively. Subsequent references to the closed and open cohorts refer to these eligibility criteria and the timeframes used to identify these patients.

Exclusions:

- 1. Patients that are recorded as no longer active in the general practice or deceased in the EMR.
- 2. Patients that are pregnant at baseline.

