2.6 Timing of final analysis and outcome assessments

Statistical analyses for the cancer-risk study will commence in September 2023 after the Statistical Analysis Plan has been uploaded to the Australian and New Zealand Clinical Trials Registry.

Primary and secondary outcomes will be assessed at the trial end date, 30th September 2022, approximately 12-months after the trial start date, 4th October 2021. Subsequent references to the trial period refer to this 12-month period. The outcomes will reflect the status of each patient at the trial end date, based on their recorded observations, investigations and/or pathology test results in the EMR.

Baseline measures of the outcome and patient characteristics will be assessed at the trial start date (4th October 2021). The baseline measures for eligible patients will be based on the history of pathology test results in the EMR, in the preceding 6 months from the 4th of October 2021 for raised PSA, and the preceding 12-months for markers of anaemia and raised platelets.

3 Statistical principles

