4.1 Primary outcome

The **primary outcome** is the proportion of eligible patients identified as at risk of undiagnosed prostate, oesophageal, gastric, colorectal, endometrial, lung or ovarian cancer that have been assessed and investigated according to NICE², Cancer Council Victoria⁴, Victorian Government Department of Health and Human Services⁸, Prostate Cancer Foundation of Australia guidelines⁵, within the 12-month trial period. The absence of any relevant recorded investigation, prescription, observation, or diagnosis during the trial period will be considered equivalent to the patient not being assessed or investigated.

The primary outcome will include any relevant investigation, dependent on whether patients were identified as at risk of cancer for iron deficiency anaemia, raised platelets or raised PSA. The relevant investigation must occur between being identified as at risk of an undiagnosed cancer (either at baseline or within the following 6 months), and the trial end date (30th Sept 2022).

For each patient identified as at risk of cancer with one or more markers of anaemia, a relevant investigation includes a repeat full blood count, iron studies, coeliac disease serology, FOBT, transvaginal ultrasound, referral to gastroenterologist, assessment of upper or lower GI symptoms and/or haematuria, prescription of an oral supplement and/or record of an iron infusion.

For each patient identified as at risk of cancer with a raised platelet count, a relevant investigation includes a repeat platelet count, chest x-ray, chest CT, FOBT, CA-125, transvaginal ultrasound, assessment for symptoms for lung, colorectal, gastro-oesophageal, ovarian or endometrial cancer, referral to a gastroenterologist, respiratory physician, or gynaecologist.

For each patient identified at risk of cancer with a raised PSA, a relevant investigation includes a repeat PSA test, free to total PSA percentage and/or referral to a urologist.

For any patient identified as at risk of cancer with more than one altered test result (e.g., anaemia and raised platelets), we will consider a relevant investigation from either marker as the equivalent of being assessed and investigated according to guidelines. In usual care, it is expected that the GP would prioritise care or use a sequential manner in responding to multiple possible investigations.

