4.4.4 Primary outcome

For the primary outcome, the odds ratio (relative measure) and the difference in proportions between the intervention and control arms (absolute measure) will be estimated using a generalised linear model (GLM) with the logit link and identity link functions, respectively, and binomial distribution for both models. Both models will include randomisation stratification factors, GP FTE and IRSD terciles as covariates, and use Generalised Estimating Equations with an exchangeable correlation structure and robust standard errors to allow for correlation of outcomes within general practice. If the model used to estimate the risk difference fails to converge, the risk difference will be derived from the GLM with the logit link function.^{11,12}

The absolute (difference in proportions between the intervention and control arms) and relative (odds ratio) estimated intervention effects for the primary outcome will be reported with 95% confidence intervals and p-values.

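### The closed-versus-open cohort subgroup in the cancer-risk SAP mixes length of follow-up with type of patient, so its interaction cannot be attributed to either

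*SAP*

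**What the plan says.** All references are to the cancer-risk SAP.

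- **Outcome window (4.1).** "The relevant investigation must occur between being identified as at risk of an undiagnosed cancer (either at baseline or within the following 6 months". Observation then runs until the trial closes.
- **Close of observation (2.6).** One calendar date applies to everyone: "trial end date, 30th September 2022, approximately 12-months after the trial start date, 4th October 2021".
- **Open cohort (2.2).** For anaemia: "Eligible patients not captured at baseline, with one or more markers of anaemia between October 4, 2021, and April 4, 2022". Raised platelets and raised PSA have the same entry dates.
- **Closed cohort (2.2).** Anaemia and platelets qualify on one abnormal result in the previous 6 months or, for anaemia, "two consecutive markers of anaemia in the past 12 months"; platelets have a parallel rule. PSA qualifies on a result in the previous 6 months.
- **No recorded action (4.5.5).** "If a relevant investigation or follow-up is not in the patient record, then they will be considered to not have received guideline concordant care". This applies however long the patient was observed.
- **Effect measures (4.4.4).** Binomial GEE models give "the odds ratio (relative measure) and the difference in proportions between the intervention and control arms (absolute measure"). Neither model has a term for follow-up time.
- **Subgroup (4.5.7).** The purpose is given as "To evaluate the shorter time for follow-up in the open cohort, we will conduct a sub-group analysis". The method adds cohort and its interaction with study arm to the same regression models.

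**The concern.** The subgroup has a stated purpose: to find out about the open cohort's shorter follow-up. The planned term compares two groups that differ in two respects at once. One is time available for an investigation to be recorded. The other is the patient's position at the start of observation: an abnormality that may have been on file for months, against one that has just appeared. The model has nothing that separates the two.

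Follow-up length also matters by itself. The odds ratio and risk difference of a cumulative proportion generally change as the window lengthens, even when the program multiplies the rate of investigation by the same factor throughout. A reader could therefore take a non-null interaction as evidence that the program works differently in new and old cases when only the windows differ. A null interaction could equally be taken as reassurance that the shorter follow-up did no harm, when two influences have cancelled.

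**Working it through.** **Step 1. Observation windows, from the dates in 2.2 and 2.6.**

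- 4 October 2021 to 30 September 2022: 361 days. This is the closed cohort, withdrawals aside, and agrees with the SAP's description of about 12 months.
- 4 April 2022 to 30 September 2022: 179 days. This is the latest open-cohort entry.
- Entry window: 361 − 179 = 182 days. If entry is uniform, mean open-cohort follow-up is (361 + 179)/2 = 270 days.

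**Step 2. Can unequal windows alone create an interaction?** The SAP gives no event rates, so these are assumptions: constant hazard λ in controls, the same hazard ratio (HR) in both cohorts, and uniform open-cohort entry. The control risk p at 361 days is varied.

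- λ = −ln(1 − p)/361
- Closed-cohort risks: p in controls; 1 − exp(−λ·HR·361) with the program
- Open-cohort risks: the average of 1 − exp(−λ·t) and of 1 − exp(−λ·HR·t) over t = 179, …, 361

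Example, p = 0.80 and HR = 1.5. λ = 1.6094/361 = 0.004458.

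- Closed: 0.800 and 0.9106. Risk difference 11.1 points; OR = (0.9106/0.0894)/(0.80/0.20) = 2.55.
- Open: 0.6915 and 0.8252. Risk difference 13.4 points; OR = (0.8252/0.1748)/(0.6915/0.3085) = 2.11.

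All cells at HR 1.5, with the odds ratios at HR 1.3 from the same formulas:

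| Control risk at 361 days | OR closed / open, HR 1.5 | Risk difference closed / open, HR 1.5 (points) | OR closed / open, HR 1.3 |
|---|---|---|---|
| 40% | 1.73 / 1.65 | 13.5 / 11.7 | 1.41 / 1.38 |
| 60% | 1.97 / 1.80 | 14.7 / 14.3 | 1.53 / 1.45 |
| 80% | 2.55 / 2.11 | 11.1 / 13.4 | 1.78 / 1.59 |
| 90% | 3.40 / 2.49 | 6.8 / 10.3 | 2.11 / 1.76 |

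At HR 1 every odds ratio is 1 and every risk difference is 0 in both cohorts, so no interaction arises.

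At 40% and 60% both scales show the smaller effect in the open cohort. At 80% and 90% the odds ratio is smaller there but the risk difference is larger, so the two planned measures disagree about which cohort benefits more. A real difference can also be hidden: at 80% control risk, an HR of about 1.64 in the open cohort against 1.5 in the closed cohort gives equal odds ratios.

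**Step 3. Does a common window remove this?** With both cohorts scored at 179 days, p = 0.80 and HR = 1.5, the risks are 0.550 and 0.698 in each cohort (risk difference 14.8 points, OR 1.89), so the spurious interaction disappears. A true difference still shows. With control risk 50% at 361 days, HR 1.5 closed and 1.25 open, the 179-day risk differences are 11.2 and 5.8 points.

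**Step 4. Does another planned analysis cover the point?** Secondary outcome 7 (4.2, 4.4.5) is time to event with censoring but is confined to the open cohort, so it cannot compare cohorts. Sensitivity analysis 1 (4.5.1) adjusts for cohort as a main effect only.

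**The case against.** The strongest reply is that the SAP makes follow-up length the question. An interaction that reflected nothing else would answer it, so a reader who infers that the analysis fails because it measures only follow-up has the argument the wrong way round. The SAP does not support that inference: the entry rules in 2.2 make the cohorts differ in the age of the qualifying result as well as in time observed. The objection rests on that mixture.

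A reader might also infer that cohort and follow-up are completely aliased. They are not. Open-cohort follow-up varies from 179 up to 361 days, and withdrawal can shorten observation in either cohort. The two are strongly related but not identical.

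Nor do the documents support an inference of biased arm comparisons. Within each cohort both arms have the same observation rule, and with no program effect the unequal windows produce no interaction. The primary estimate is untouched.

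Size is a fair point as well. The large gaps need both a high control risk and a sizeable effect, and the SAP states neither. If most action follows quickly after an abnormal result, more of it falls inside 179 days and the gaps narrow. Section 4.5.7 also promises summary statistics by subgroup and arm, so differing base rates will be visible.

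These points limit the concern. They leave standing that no common window or time term is planned, so the interaction has no single interpretation.

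**Conclusion.** The point holds in a limited form. The planned interaction combines a difference in observation time (361 against 179 to 361 days) with a difference between older and new abnormal results, and cannot be attributed to either. It therefore does not serve the purpose given in 4.5.7. If the program has an effect, the windows alone can generate an interaction. Under constant hazard, uniform entry and a common HR of 1.5, the ratio of open to closed odds ratios runs from about 0.96 at 40% control risk (1.65/1.73) to 0.73 at 90% (2.49/3.40), and the risk-difference contrast changes sign. It is small at low to moderate control risk, smaller at HR 1.3, and absent at HR 1. The day counts are exact; the effect sizes are illustrations, because the SAP gives no event rates. The analysis is exploratory, so the priority is modest.

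**What to change.** In 4.5.7:

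1. Fit the cohort-by-arm interaction on the primary outcome scored within 179 days of identification in both cohorts, counted from 4 October 2021 for the closed cohort and from the index abnormal result for the open cohort. Withdrawals aside, every patient entering by 4 April 2022 has 179 days before the trial ends.
2. To examine follow-up length, compare the closed-cohort intervention effects at 179 and 361 days. The patients are the same at both times, so cohort type does not enter.
3. State that any cohort difference remaining after step 1 may reflect older versus new abnormal results.

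The cost is a few lines of SAP text and one derived variable, from dates already needed to apply the outcome definition in 4.1. The downside is that actions after day 179 are not used in the cohort contrast. The primary analysis stays as planned.

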4.6 Statistical software and technical details

All analyses will be conducted using Stata Statistical software (v17).⁹ Appendix B Table 1, 2 and 3 provide the proposed template for the statistical analysis of the primary and secondary outcomes. These results may also be presented graphically, where appropriate. Any post-hoc explanatory analyses not identified in the SAP will be clearly identified in the final statistical report. Any deviations from the planned analyses detailed in the SAP will be documented and reported in a revised version of this SAP.

5 References

- 1 Campbell, M. K., Piaggio, G., Elbourne, D. R. & Altman, D. G. Consort 2010 statement: extension to cluster randomised trials. *British Medical Journal* **345**, e5661, doi:10.1136/bmj.e5661 (2012).
- 2 NICE. Suspected cancer: recognition and referral. NICE guideline [NG12] 2017. Available from: https://www.nice.org.uk/guidance/ng12/chapter/Recommendations-organised-by- symptom-and-findings-of-primary-care-investigations#primary-care-investigations.
- 3 Victorian Government Department of Health and Human Services. Upper gastrointestinal endoscopy categorisation guidelines for adults 2018. 2018, Victorian Government Department of Health and Human Services: Melbourne.
- Cancer Council Victoria, University of Melbourne, and Victoria State Government.
 Implementing PAthways for Cancer Early Diagnosis: I-PACED lung cancer resource card.
 21/4/2020]. Available from: https://www.cancervic.org.au/downloads/health-professionals.
- 5 Prostate Cancer Foundation of Australia and Cancer Council Australia. Clinical Practice Guidelines on PSA Testing. 21/4/2020]. **Available from:** https://www.prostate.org.au/media/611412/PSA-Testing-Guidelines-Overview.pdf.
- 6 Victoria State Government. Department of Health and Human Services. Colonoscopy categorisation guidelines 2017 Explanatory notes.
- 7 Pasricha, S. R. S. *et al.* Diagnosis and management of iron deficiency anaemia: a clinical update. *Medical Journal of Australia* **193**, 525-532 (2010).
- 8 Department of Health and Human Services State Government of Victoria and Cancer Council. Optimal care pathway for men with prostate cancer. Department of Health and Human Services - State Government of Victoria, Editor. 2014.
- 9 Stata Statistical Software: Release 17. (College Station, TX: StataCorp LLC.; 2021).
